6.1.4 Application Device

The application device is commercially available in the US, Canada and several European countries. It is not considered as an investigational product. Depending on its regulatory status, the product will be labelled according to local regulatory requirements, and may contain the following information:

- Name and address of manufacturer;
- Protocol number; and
- Statement that the product is limited for clinical trial use only.

6.1.5 Accessory Tips

The accessory tips are commercially available in the US, Canada and several European countries. They are not considered as an investigational product. There will be the following accessory tips provided for use with the application device:

- 35 cm rigid tips;
- 45 cm flexible tips;
- Airless Spray Accessory
- 4 cm tip (control tip)

Any of the above mentioned accessory tips may be used, according to surgeon preference. Tips should be used in accordance with their Product Assembly Guide.

6.1.6 Pressure Regulators

Only ETHICON/Omrix pressure regulators may be used. The pressure regulators may be provided when commercially available. They will be used according to their intended Instructions for Use/Investigator Brochure and are not considered as an investigational product.

6.1.7 Preparation

The two frozen components of EVICEL® (BAC2 and Thrombin) must be thawed before use, using one of the following methods:

- 2-8°C (refrigerator): vials thaw within one day; or
- 20-25°C (room temperature): vials thaw within one hour; or
- 37°C; vials thaw within ten minutes and should not be left at 37°C for more than 10 minutes. The temperature must not exceed 37°C.

Thawed, unopened vials must be stored, at the temperature range stated within the Package Leaflet. Thawed vials must not be re-frozen.

Before use, the product must reach 20-30°C.

After thawing, preparation of the product must occur in a sterile surgical field. The two components should be drawn into the application device, following directions enclosed in the application device package. Both syringes must be filled with equal volumes, and should not contain air bubbles. Selection of the appropriate application tip will be left to the discretion of the surgeon.

6.1.8 Dose, Route and Duration of Administration

For each subject, at least one kit of EVICEL® (BAC2 and Thrombin) will be thawed and available for administration prior to randomization. EVICEL® will be sprayed or dripped onto the tissue to produce a thin, even layer. A cure time of 1-2 minutes should be allotted between applications to allow for polymerisation. The amount of EVICEL® required depends upon the area of tissue to be treated and the method of application.

EudraCT Number: 2013-003401-26 Page 17 of 35

Amendment 4: 08 January 2018

Application can be made by dripping or spraying in accordance with the EVICEL® Investigator Brochure, Accessory Tip Directions and Device and Pressure Regulator Instructions for Use.

6.2 Investigational Product Dispensation and Accountability

A dispensing log will be kept by the designated study personnel. This log will contain information on the date of administration, subject ID and quantity of EVICEL® dispensed, details of any remaining product, and subsequent destruction. The study monitor will verify these logs during the course of the study.

6.3 SURGICEL® (Control Group)

For this study, SURGICEL® will be provided by the Sponsor and must be used according to the Instructions for Use.

6.4 Concomitant Medications

6.4.1 Topical Haemostats

The use of any other Topical Absorbable Haemostat (TAH) will be permitted as outlined in section 7.1.3.4 below.

Other haemostasis products, including Topical Absorbable Haemostat (TAH) and fibrin sealants, may be used at additional bleeding sites other than the TBS as necessary during the 10 minute haemostasis assessment period.

Details of all Topical Absorable Haemostats used for the subject throughout the procedure will be recorded on the Concomitant Medication eCRF.

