If additional soft tissue or parenchymal organ bleeding sites are identified, the surgeon may treat with the same treatment product according to the subject's randomization assignment, if clinically appropriate or their preferred standard of care. Haemostatic assessment of these additional bleeding sites will not be recorded.

TEST PRODUCT:

EVICEL® Fibrin Sealant (Human)

STUDY POPULATION:

Paediatric subjects, undergoing non-emergent abdominal, retroperitoneal, pelvic or thoracic (non-cardiac) surgery procedures, wherein an appropriate TBS is identified. Paediatric subjects for this study are defined as:

- Neonates (birth to 30 days) with pre-term neonates born ≤37 weeks gestation included within this group;
- Infants and toddlers (31 days to <24 months);
- Children (2 to 11 years); and
- Adolescent (12 to 18 years).

CONFIDENTIAL

Protocol: 400-12-006 Amendment 4: 08 January 2018

PRIMARY ENDPOINT:	Absolute time to haemostasis, defined as absolute time when there is no detectable bleeding at the Target Bleeding Site (TBS).
SECONDARY ENDPOINTS:	 Haemostasis at 4, 7 and 10 minutes following randomization; Incidence of treatment failures (defined as haemostasis not achieved within 10 minutes or bleeding at the TBS during the ten-minute observational period that requires further haemostatic measures other than re-application of the assigned haemostatic adjunct); Incidence of adverse events (including thrombotic events and events associated with TBS re-bleeding); Proportion of subjects with no- rebleeding; and Haemoglobin, Haematocrit, Platelets, Volume of blood loss, Volume of blood and blood products transfusions.
SAFETY:	Adverse events will be collected from time of randomization, throughout the follow-up period of 30 (± 14) days. Intra-operative bleeding at the TBS after 10 minutes will be an adverse event.

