6 INVESTIGATIONAL PRODUCT AND CONTROL GROUP

6.1 EVICEL® (Treatment Group)

6.1.1 Formulation

EVICEL® is a human plasma-derived fibrin sealant. EVICEL® consists of two components: a concentrate of Human Clottable Protein (referred to as Biological Component 2; BAC2) and a solution of Human Thrombin. No material of animal origin is present in the product. A purpose-designed application device is used to apply EVICEL® to the surgical site by spraying or dripping. Said device has been designed to ensure even mixing of the two components.

Composition of EVICEL®

	Component 1(Clottable protein)	Component 2 (Thrombin)
Active Ingredient	Concentrate of human clottable protein (containing mainly human fibrinogen)	Human Thrombin
Other Ingredients	Arginine hydrochloride, Glycine, Sodium chloride, Sodium citrate, Calcium chloride, Water for injection (WFI)	Calcium chloride, Human albumin, Mannitol, Sodium acetate, Water for Injection (WFI)

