- In the event of bleeding at the TBS during the 10 minute observational period (in either EVICEL® or SURGICEL treatment group) that requires further and immediate haemostatic measures other than re-application of the assigned haemostatic adjunct (EVICEL® or SURGICEL®), the surgeon should perform these measures, and the subject will be a failure for the secondary endpoint "incidence of treatment failures".
- If haemostasis is not achieved by the end of the 10 minute observational period, the surgeon may then apply the use of further haemostatic measures according to his/her preference, and record the subject as a treatment failure.
- If additional soft tissue or parenchymal organ bleeding sites are identified, the surgeon may treat with the same treatment product according to the subject's randomization assignment, if clinically appropriate. Time to haemostasis does not need to be recorded for these additional bleeding sites. However if a subject is randomised to SURGICEL® treatment group, EVICEL® should not be used to treat any other soft tissue bleeding sites. There is no restriction on the use of SURGICEL® in the EVICEL® treatment group to treat other bleeding sites. SURGICEL® must be used per its instructions for use.

EudraCT Number: 2013-003401-26 Page 21 of 35

Amendment 4: 08 January 2018

• If re-bleeding at the TBS occurs after the 10-minute haemostatic assessment period, this can be treated with the randomised study product or the surgeon's standard of care and **must be recorded** as an adverse event.

- Any additional treatments at the TBS at any time during the procedure whether it be the randomized treatment or other clinically appropriate treatments will be recorded, including time and method of retreatment.
- Number of EVICEL® kits used; or Number of SURGICEL® product kits used and standard of care treatments (if applicable) will be recorded.

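### Protocol 6.4.1, 7.1.3.4 and the synopsis give different rules on fibrin sealant at other bleeding sites in SURGICEL subjects, and the SAP does not identify subjects exposed in this way

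*Protocol*

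**What the plan says.** Three places in the Protocol govern what may be used at bleeding sites other than the TBS.

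- Section 6.4.1 (Topical Haemostats): "Other haemostasis products, including Topical Absorbable Haemostat (TAH) and fibrin sealants, may be used at additional bleeding sites other than the TBS". The sentence goes on to limit this to need during the 10-minute assessment period. It does not distinguish the arms and makes no exception for the study product.
- Section 7.1.3.4 (Haemostasis Assessment): "However if a subject is randomised to SURGICEL® treatment group, EVICEL® should not be used to treat any other soft tissue bleeding sites". For the opposite direction: "There is no restriction on the use of SURGICEL® in the EVICEL® treatment group to treat other bleeding sites". Neither sentence has a time limit.
- Synopsis, Procedure: additional soft tissue or parenchymal sites may be treated with the assigned product "according to the subject's randomization assignment, if clinically appropriate or their preferred standard of care". The restriction in 7.1.3.4 is not repeated.

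Two other sections bear on the reading. Section 6.1.1 says "EVICEL® is a human plasma-derived fibrin sealant", which places EVICEL in the class that 6.4.1 permits. Section 7.1.3.2 requires unused EVICEL to leave the sterile field at once when a subject is randomized to SURGICEL.

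On recording, the last sentence of 6.4.1 sends details of topical absorbable haemostats (TAHs) to the Concomitant Medication eCRF. It does not name fibrin sealants, although the sentence before it lists the two separately.

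SAP section 5 covers subjects who received the other treatment instead of the assigned one. It has no rule for a subject who received both. SAP section 7 and Table 14.1.3.7 summarise additional treatment at the TBS only.

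**The concern.** The same act can be allowed, discouraged or left open depending on which section a site consults. If a SURGICEL subject is given a fibrin sealant at a second site, that subject carries exposure to the test product or its class, but every planned safety table counts the subject as SURGICEL.

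This matters for outcomes measured on the whole child: adverse events, thrombotic events, haemoglobin, haematocrit, platelets, blood loss and transfusion volumes. Safety is a stated objective, and SAP section 9.4 summarises adverse events by treatment received. A thrombotic event in such a subject would appear in the control column, and no planned table would show that the subject had also received fibrin sealant.

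**Working it through.** No figure in the plan needs reproducing, so the check is mainly a comparison of text. The cases are a SURGICEL subject treated at a non-TBS site within the 10 minutes:

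| Product and site | 6.4.1 | 7.1.3.4 | Synopsis |
|---|---|---|---|
| EVICEL, soft tissue | permitted on its face | should not be used | open (standard of care) |
| EVICEL, parenchymal organ | permitted on its face | not covered by the restriction | open |
| Another fibrin sealant, either tissue | permitted | not covered by the restriction | open |

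**Direct conflict.** Only the first row is a head-on conflict, between 6.4.1 and 7.1.3.4. The other two rows are gaps. The bullet in 7.1.3.4 opens by naming both soft tissue and parenchymal sites, yet its restriction names soft tissue alone. After 10 minutes the permission in 6.4.1 no longer applies, but the difference between 7.1.3.4 and the synopsis remains.

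**Narrower reading.** Suppose the opening words of the 6.4.1 sentence mean products other than the two study products. Row 1 then resolves between 6.4.1 and 7.1.3.4, and removal of unused EVICEL under 7.1.3.2 makes row 2 less likely in practice. Row 3 is unchanged: another fibrin sealant is still allowed in control subjects. The synopsis still carries no restriction.

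**Opposite direction.** The sentence on SURGICEL in the EVICEL arm conflicts with nothing. It does show that the rule is asymmetric, so a reconciled statement has to address both arms.

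**Which endpoints are exposed.** Protocol 7.1.3 makes the TBS the only site evaluated for time to haemostasis. Haemostasis at 4, 7 and 10 minutes and treatment failure are also judged at the TBS. The endpoints in SAP section 9.1 other than treatment failure and TBS re-bleeding belong to the whole subject.

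**Scale.** Inputs: at least 40 subjects at 1:1 (Protocol 8.1), so 40 / 2 = 20 per arm. The documents give no rate for fibrin sealant use at other sites, so the rate p below is assumed.

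- Share of the control arm per exposed subject: 1/20 = 5%; 2/20 = 10%; 4/20 = 20%.
- Chance of at least one exposed subject among 20: 1 − (1 − p)^20.
  - p = 5%: 1 − 0.95^20 = 0.642, or 64%
  - p = 10%: 1 − 0.90^20 = 0.878, or 88%
  - p = 20%: 1 − 0.80^20 = 0.988, or 99%
- One thrombotic event in one exposed control subject, with no others in the arm, moves control incidence from 0/20 = 0% to 1/20 = 5%.

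**The case against.** The strongest defence is that the passages can be read together. Section 6.4.1 sits under Concomitant Medications, apart from the sections on the two study products, so its permission may be meant for other products only. The sentence before it refers the reader to 7.1.3.4 for TAH use. Section 7.1.3.2 takes unused EVICEL off the field and is not limited to soft tissue. This has weight and narrows the conflict. It does not remove it: 6.4.1 does not state the exclusion, its fibrin sealant sentence carries no cross-reference, the synopsis is silent, and other fibrin sealants remain allowed in control subjects.

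A second defence is traceability. EVICEL is logged by subject ID (Protocol 6.2). Use against 7.1.3.4 would be a deviation and could appear in Table 14.1.1.3. Concomitant medications are listed by subject. Protocol 7.1.3.4 also asks for standard of care treatments to be recorded where applicable, without saying at which sites. This also stands in part. But use that the Protocol permits is not a deviation, and the general rule in 6.4.2 may capture a non-study fibrin sealant without assuring it. A reader might infer that the data are already recorded; the recording sentence in 6.4.1 does not support that.

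Third, the safety summaries are descriptive, and SAP section 9.4 plans no inference. That is correct, so the point concerns how a small table will be read and does not affect any test.

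**Conclusion.** The point holds as an inconsistency within the Protocol, with a gap in recording and reporting. The SAP does not contradict the Protocol here; it is silent.

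Two stronger inferences are tempting and not supported. One is that the primary or other TBS endpoints are biased; they are assessed at the TBS and are not directly affected. The other is that the between-arm safety difference shrinks by a known fraction equal to the share of control subjects exposed. The documents give no such share, and the calculation would also assume that sealant used elsewhere carries the full effect of assigned EVICEL.

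What can be said about size is limited. Each exposed control subject is 5% of a 20-subject arm. At assumed exposure rates of 5% to 20%, the chance that at least one control subject is affected is 64% to 99%. This rests on 20 subjects per arm and on independent use across subjects. The change is worth making because it is cheap and safety is a stated objective.

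**What to change.** 1. **Protocol.** Reconcile 6.4.1, 7.1.3.4 and the synopsis into one statement that covers both arms, both soft tissue and parenchymal non-TBS sites, and both EVICEL and other fibrin sealants. Which clinical rule is right is for the sponsor and investigators and is not judged here.
2. **Recording.** Extend the recording sentence in 6.4.1 to name fibrin sealants as well as TAHs.
3. **SAP section 9.** Report, for each arm, the number of subjects exposed to any fibrin sealant outside the TBS. Flag those subjects in the adverse event and thrombotic event listings. Keep the full Safety set as the main summary.

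Do not add a version of the control-arm tables that leaves out exposed subjects. The exposure arises after randomization and is probably related to how much the child bleeds. Dropping those subjects from one arm could remove its heavier bleeders and make its blood loss and transfusion look better.

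Cost: a protocol clarification, one extra recorded item, and a flag whose counts will be small.

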6.4.2 Documentation of Concomitant Medications

Indication and start-stop dates of concomitant medications administered from 24 hours prior to surgery up to the follow up contact or evaluation will be recorded. This will include medications that patients are using chronically.

Anaesthetics used for surgery and over the counter (OTC) drugs will not be recorded as concomitant medication (with the exception of prophylactic aspirin, which should be documented). Concomitant medications used to treat Adverse Events must also be documented.

7 STUDY EVALUATIONS

7.1 Study Procedures

The schedule of events included in the synopsis summarises the frequency and timing of the study procedures. Data collected for the subject during the study will be recorded in the subject's medical records, and study worksheets/source documents, as appropriate, and transcribed into the eCRF.

7.1.1 Screening (Within 21 Days Prior to Surgical Procedure)

Prospective subjects will be screened within 21 days prior to surgery. Screening and baseline visits may occur at the same time. Prior to any study related procedures, subjects and/or parent or legal

EudraCT Number: 2013-003401-26 Page 18 of 35

Amendment 4: 08 January 2018

representative will be fully informed of all aspects of the study. Subjects and/or their parent or legal representative will be asked to sign a Consent Form or assent as applicable.

The following tests and activities will be performed at the screening visit unless existing data from within 21 days prior to surgery is available, in which case the test/activity will not be repeated. The timing of these activities may occur based on routine hospital practice but may be done up to the day of, but prior to, surgical procedure. If blood tests required at screening are performed, only the result closest to the date of surgery will be collected.

- Informed consent/assent process, as applicable;
- Allocation of screening number;
- Review of Inclusion / Exclusion criteria to confirm subject pre-operative eligibility;
- Documentation of demography information;
- Physical examination as per institutions normal procedure;
- Documentation of relevant medical and surgical history;
- Full blood count (FBC) with differential (samples taken closest to surgery date will be recorded);
- Coagulation parameters to include prothrombin (PT), activated partial thromboplastin time (aPTT), International Normalised Ratio (INR) (samples taken closest to surgery date will be recorded);
- In the event that a subject is not eligible, the reason will be documented on the screening log.

7.1.2 Baseline Assessments (Within 24 Hours Prior to Procedure)

The following activities will be performed within 24 hours prior to the procedure. The timing of these activities may occur based on routine hospital practice.

- Review of inclusion / exclusion criteria to confirm subject pre-operative eligibility. In the event that
 a subject is not eligible, the reason will be documented on the source documentation and screening
 log.
- Documentation of all concomitant medications starting 24 hours prior to surgery. (See Section 6.4)
- Documentation of any changes in medical history from the screening visit.
- Serum or urine pregnancy test (if applicable)

Note: At least one Full Blood Count (FBC) with differential, coagulation parameter testing and pregnancy test (if applicable) are needed pre-procedure. If pre-operative blood tests are repeated, only the test closest to the date prior to surgery will be collected.

7.1.3 Surgical Procedure

The surgeon will use his/her standard surgical techniques for the surgical procedure. The TBS will be identified, and will be the only specific site or region to be evaluated for time to haemostasis in this clinical study. The following activities will be performed, and information will be collected, during the surgical procedure:

- Details of procedure including operating room/theatre time, procedure time, estimated blood loss and transfusion information (blood and blood products) (if applicable);
- Documentation of concomitant medications; and
- Adverse events from start of randomization, including any complications potentially related to bleeding and/or thrombotic events.

EudraCT Number: 2013-003401-26 Page 19 of 35

Amendment 4: 08 January 2018

7.1.3.1 Pre-Randomization Procedures

EVICEL® and SURGICEL® will be prepared and available in the sterile field of the operating room, ready for administration for each patient. The investigator will perform the surgical procedure according to their standard practice.

When the surgeon encounters the first appropriate TBS with mild/moderate bleeding in the soft tissue or a parenchymal organ related to the primary operative procedure where conventional methods of control (i.e. suture, ligature, cautery) are ineffective or impractical, the subject can be considered for randomization. The following information will be recorded:

- Intra-operative confirmation of eligibility and classification of the target bleeding site (TBS);
- TBS location information, e.g. abdominal, pelvic, retroperitoneal, or thoracic (non-cardiac);
- TBS tissue type, e.g. loose areolar connective tissue, fat, lymphatic tissue/lymph node beds, muscle or other (specify); and
- TBS organ type, e.g. kidney, liver, spleen or pancreas;
- Type of bleeding, e.g. mild or moderate.

7.1.3.2 Randomization

Once intra-operative eligibility is confirmed and the TBS identified, the appropriate randomization envelope will be opened, randomization treatment called out and the stopwatch will be started. The time of randomization will be recorded (by the wall clock using 24-hour clock), this will be considered T_0 .

If the subject is randomized to SURGICEL®, the unused EVICEL® treatment product **MUST** immediately be removed from the sterile field. After the procedure, accountability of the product should be documented.

If the subject is randomized to EVICEL®, the unused SURGICEL® control treatment product **MUST** immediately be removed from the sterile field. After the procedure, accountability of the product should be documented.

7.1.3.3 Treatment Application

The following procedures must be followed following randomization:

- Subjects assigned to EVICEL® should have a thin, even layer of EVICEL® applied by either dripping or spraying the product in accordance with the Investigator Brochure; or
- Subjects assigned to SURGICEL® should have SURGICEL® applied on the TBS, according to the product Instructions for Use.

7.1.3.4 Haemostasis Assessment

After placement of the assigned study treatment (EVICEL® or SURGICEL®), there will be an observation period during which the TBS will be assessed at 4, 7 and 10 minutes from randomization and for absolute time for haemostasis. **SURGICEL® must not be lifted or disturbed when assessing for haemostasis.** Once haemostasis has been achieved, excess SURGICEL may be removed according to the IFU assuring that the clot is not disturbed to avoid potential rebleeding. For additional details consult the IFU Contraindications, Warnings and Precautions sections.

EudraCT Number: 2013-003401-26 Page 20 of 35

CONFIDENTIAL

Protocol: 400-12-006 Amendment 4: 08 January 2018

• Absolute time to haemostasis (TTH from the time of randomization) is recorded once haemostasis

	is achieved. Haemostasis will be defined as no detectable bleeding from the TBS.	
•	Haemostasis is also assessed at the specified time-points (4 7 and 10 minutes following	

•	Haemostasis	İS	also	assessed	at	the	specified	time-points	(4,	7	and	10	minutes	following
	randomizatio	n),	which	h is outline	ed ii	n the	following	timetable:						

T ₀	Start time when randomization envelope is opened
T _{APP}	Time when randomised haemostatic product (EVICEL® or SURGICEL®) is initially applied
T ₄	TBS Bleeding assessment 4 minutes following randomization.
T ₇	Bleeding is assessed 7 minutes after randomization
T ₁₀	Bleeding is assessed 10 minutes after randomization
T _{ABS}	Exact time when absolute haemostasis has been achieved

If haemostasis is achieved before four minutes (<4 min.) after randomization, the absolute time to haemostasis must be recorded.

- If haemostasis is achieved between four and seven minutes (>4 and <7 min.) after randomization, the absolute time to haemostasis must be recorded.
- If haemostasis is achieved between 7 and ten minutes (>7 and <10 min.) after randomization, the absolute time to haemostasis must be recorded.
- If haemostasis is achieved after 10 minutes, this absolute time to haemostasis must be recorded.

Haemostasis Scenarios

- If breakthrough bleeding occurs at the TBS during the 10-minute treatment period, the surgeon may re-treat with the randomised study product, if clinically appropriate. If the subject is randomised to EVICEL®, re-treatment must be performed according to the Investigator Brochure.
- In the event of bleeding at the TBS during the 10 minute observational period (in either EVICEL® or SURGICEL treatment group) that requires further and immediate haemostatic measures other than re-application of the assigned haemostatic adjunct (EVICEL® or SURGICEL®), the surgeon should perform these measures, and the subject will be a failure for the secondary endpoint "incidence of treatment failures".
- If haemostasis is not achieved by the end of the 10 minute observational period, the surgeon may then apply the use of further haemostatic measures according to his/her preference, and record the subject as a treatment failure.
- If additional soft tissue or parenchymal organ bleeding sites are identified, the surgeon may treat with the same treatment product according to the subject's randomization assignment, if clinically appropriate. Time to haemostasis does not need to be recorded for these additional bleeding sites. However if a subject is randomised to SURGICEL® treatment group, EVICEL® should not be used to treat any other soft tissue bleeding sites. There is no restriction on the use of SURGICEL® in the EVICEL® treatment group to treat other bleeding sites. SURGICEL® must be used per its instructions for use.

EudraCT Number: 2013-003401-26 Page 21 of 35

Amendment 4: 08 January 2018

• If re-bleeding at the TBS occurs after the 10-minute haemostatic assessment period, this can be treated with the randomised study product or the surgeon's standard of care and **must be recorded** as an adverse event.

- Any additional treatments at the TBS at any time during the procedure whether it be the randomized treatment or other clinically appropriate treatments will be recorded, including time and method of retreatment.
- Number of EVICEL® kits used; or Number of SURGICEL® product kits used and standard of care treatments (if applicable) will be recorded.

